6.1.3 Serious Adverse Event Reporting to Supporting Company Exelixis

As soon as an investigator becomes aware of an AE that meets the definition of 'serious,' this should be documented to the extent that information is available.

- Investigator shall notify Exelixis within twenty-four (24) hours of making such discovery by submitting the completed SAE report form and any other pertinent SAE information as indicated on the SAE reporting form;
- This report must be submitted by Institution to Exelixis at e-mail: [contact] or [contact], even if it is not felt to be drug related;
- Pregnancy (for a subject or for the partner of a subject), although not itself an SAE, should also be reported on an SAE form or pregnancy form and be followed up to determine outcome, including spontaneous or voluntary termination, details of birth, and the presence or absence of any birth defects or congenital abnormalities;
- SAEs that must be recorded on an SAE Reporting form include the following:
 - o all SAEs that occur after informed consent and through 30 days after the decision to discontinue study treatment (or the date the subject is deemed to be a screen failure);
 - any SAEs assessed as related to study treatment or study procedures, even if the SAE occurs more than 30 days after the decision to discontinue study treatment;
 - although most hospitalizations necessitate reporting of an SAE, some hospitalizations do not require SAE reporting, as follows: elective or

previously scheduled surgeries or procedures for pre-existing conditions that have not worsened after initiation of treatment (eg, a previously scheduled ventral hernia repair); pre-specified study hospitalizations for observation; or events that result in hospital stays of fewer than 24 hours and that do not require admission (eg, an emergency room visit for hematuria that results in a diagnosis of cystitis and discharge to home on oral antibiotics). SAEs must, however, be reported for any surgical or procedural complication resulting in prolongation of the hospitalization.

6.1.4 Regulatory Reporting

All serious unexpected adverse drug reactions (unexpected related SAEs) must be reported to the Food and Drug Administration (FDA) as required by 21 CFR 312.32:

- These reports are to be filed utilizing the MD Anderson Cancer Center Internal SAE Report Form for Prompt Reporting;
- The MD Anderson Cancer Center Internal SAE Report Form for Prompt Reporting must be submitted by the study site to Exelixis within one to two business days of submission to the FDA to allow Exelixis time to cross-report to Exelixis' IND. E-mail: [contact]; [contact].

6.2 Other Safety Considerations

6.2.1 Laboratory Data

All laboratory data required by this protocol and any other clinical investigations should be reviewed. Any abnormal value that leads to a change in subject management (eg, dose reduction or delay or requirement for additional medication or monitoring) or that is considered to be of clinical significance by the investigator should be reported as an AE or SAE as appropriate.

6.2.2 Pregnancy

If a subject becomes pregnant during the study, she will be taken off study treatment and will be followed through the end of her pregnancy. The investigator must inform the MD Anderson Cancer Center/IND Office of the pregnancy. Forms for reporting pregnancies will be provided to the study sites upon request. The outcome of a pregnancy (for a subject or for the partner of a subject) and the medical condition of any resultant offspring must be reported to Exelixis or designee. Any birth defect or congenital anomaly must be reported as an SAE, and any other untoward events occurring during the pregnancy must be reported as AEs or SAEs, as appropriate.

6.2.3 Medication Errors/Overdose

Any study drug administration error or overdose that results in an AE, even if it does not meet the definition of serious, requires reporting within 24 hours to Exelixis or designee.

6.2.4 Follow-Up of Adverse Events

Any related SAEs or any AEs assessed as related that led to treatment discontinuation, including clinically significant abnormal laboratory values that meet these criteria, ongoing 30 days after the decision to discontinue study treatment must be followed until either resolution of the event or determination by the investigator that the event has become stable or irreversible. This follow-up guidance also applies to related SAEs that occur > 30 days after the decision to discontinue study treatment. The status of all other continuing AEs will be documented as of 30 days after the decision to discontinue study treatment.

7 STATISTICAL CONSIDERATIONS

This Phase II study's primary objective is to estimate the best overall response rate in patients with measurable disease. Response will include RECIST 1.1 CR, PR, and SD. With 14 patients, the 95% confidence interval for a 45% response rate would be (18.9, 71.1%). For the exploratory objective in the small group of patients with bone metastases, the 95% confidence interval for a 45% response rate with 8 patients would be (10.5, 79.5%). We do not include a formal statistical monitoring rule for toxicity given the established safety profile of this drug.

Continuous variables will be summarized using descriptive statistics such as mean, standard deviation, median and range. Categorical variables will be tabulated by frequencies and the corresponding percentages. Response rates and their 95% confidence intervals will be estimated. Kaplan Meier survival curves will be used to estimate survival outcomes. Cox proportional hazards regression analysis may be used to assess the association between survival and covariates of interest. The Fisher's exact test or logistic regression analysis will be used for any binary outcomes. T-tests or Wilcoxon rank sum tests will be used to compare continuous variables. Longitudinal models may be explored to study change over time.

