A recently published retrospective intention-to-treat study described potential clinical benefits derived from sunitinib in patients with metastatic PHs and PGs⁷. Seventeen patients with progressive disease over a period of 6 months were treated with 37.5-50 mg of sunitinib daily, 4 weeks on, 2 weeks off. Patients were followed with radiographic and biochemical studies every 2 to 3 months. As per RECIST 1.1, 8 patients (47%) exhibited clinical benefits: 3 patients had partial responses and 5 had prolonged stabilization of disease, including 4 patients with extensive skeletal metastases (but not other metastases) identified by18F-FDG-PET/CT scan. The tumors that responded to treatment also exhibited more than 30% reduction in glucose uptake 2-3 months after initiation of treatment compared with baseline. Patients who experienced partial response or prolonged stabilization of disease improved blood pressure and some discontinued treatment with antihypertensive medications. Most patients who benefited from sunitinib carried SDHB mutations. Unfortunately, most patients who experienced clinical benefits, later developed tumor progression⁷.

Hypothesis

Development of tumor progression and resistance to sunitinib may be related to the compensatory activation of molecular pathways that are not inhibited by this drug, such as the c-MET receptor pathway. MET and VEGFRs cooperate to promote tumor angiogenesis and MET upregulation may occur as a response to the VEGFs pathway inhibition leading to tumor resistance and growth8. MET activation is a common feature of human tumors and it is frequently observed in patients with bone metastases⁸. Molecular analyses of malignant PHs and PGs from a few patients participant of phase one clinical trials have found c-MET receptor gene mutations (unpublished data). Cabozantinib is a tyrosine kinase inhibitor with antiangiogenic and antitumor activity that targets the VEGF, c-MET, and RET receptors. This drug has been recently approved for the treatment of progressive metastatic medullary thyroid carcinoma another neuroendocrine tumor⁹. Of interest, cabozantinib has also shown effectiveness in patients with castration resistant prostate, breast, and renal cell carcinomas metastatic to the skeleton^{10, 11, 12}. Therefore, simultaneous inhibition of MET and VEGFRs by cabozantinib may provide a broad spectrum of antineoplastic activity and prevent tumor resistance in patients with malignant PHs and PGs.

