Study XL184-301 (EXAM trial) is a blind, multicenter, controlled trial for subjects with unresectable, locally advanced or metastatic MTC. In this study, 330 subjects with unresectable, locally advanced or metastatic MTC were randomized 2:1 to receive either cabozantinib 140 mg (175 mg malate salt weight) or placebo administered qd in a doubleblinded fashion (219 cabozantinib, 111 placebo). Subjects were required to have documented radiographic disease progression per mRECIST within 14 months prior to randomization. The primary objective of this study was to determine PFS in subjects treated with cabozantinib compared with placebo. Key secondary objectives were to evaluate overall response rate and OS. An IDMC evaluated interim safety and efficacy data from this study to protect subject welfare and to identify issues and provide recommendations regarding the study design and conduct. Enrollment in this study has been completed. Of the enrolled subjects, 323 received study treatment (214) cabozantinib, 109 placebo). In October 2011, the study was unblinded and the data analyzed and assessed for the primary endpoint. At the data cut-off date for the primary analysis of efficacy and safety, 113 subjects (98 cabozantinib, 15 placebo) were still on study treatment. A subsequent 120-Day Safety Report (XL184-301 Safety Addendum) was generated with a data cut-off date of 31 December 2011; at that data cut-off there were 73 subjects (65 cabozantinib, 8 placebo) still on study treatment.

The median PFS was significantly longer in the cabozantinib-treated patients (11.2 months) compared with the placebo group (4.0 months) with a response rate of 28% for cabozantinib but 0% in placebo-treated patients. Responses were observed regardless of

RET mutation status and correlations of radiologic response were made with changes in calcitonin and CEA levels from baseline²⁶. Findings from this study led to the approval of cabozantinib in the US by the FDA in November 2012 for patients with progressive, metastatic MTC.

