5.5 Tumor Measurements

Tumor response should be assessed at a frequency of 8 weeks for the first 52 weeks (and then every 12 weeks after that) by CT/MRI and based on RECIST 1.1. In patients with bone metastases, an FDG-PET scan will be obtained every 8 weeks for the first 52 weeks (and then every 12 weeks after that). Subjects continuing to show benefit (complete response [CR], partial response [PR], or stable disease [SD]) may continue on study. Subjects with PD should have their treatment discontinued (unless the investigator, with approval of the Medical Monitor, judges the patient is deriving clinical benefit), and they should enter the post-treatment phase of the study. The same method for tumor assessment should be employed at every assessment.

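### The primary response rate counts stable disease of any duration, so one stable week-8 scan makes a responder and the estimate is hard to interpret

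*Combined protocol and SAP*

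**What the plan says.** The synopsis (Statistical Methods), Section 2.2.1 and Section 7 all make the best overall response rate in measurable disease the primary objective, and all add: "Response will include RECIST 1.1 CR, PR, and SD". None of them gives a minimum duration for SD, a landmark time or a confirmatory scan, and no other section supplies one.

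On timing, Section 5.5 says: "Tumor response should be assessed at a frequency of 8 weeks for the first 52 weeks". Table 5-1 carries the same 8-week interval in its footnote. The first scheduled scan at which SD can be recorded is therefore week 8, and week 24 is the third.

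For size, Section 7 gives a 95% interval of 18.9% to 71.1% around a 45% rate with 14 patients. It gives no source for the 45%, no null rate and no success criterion. The only treatment result in this disease is the sunitinib series in Section 1.1, where "8 patients (47%) exhibited clinical benefits: 3 patients had partial responses and 5 had prolonged stabilization of disease", out of 17 treated.

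**The concern.** Best overall response takes the best category a patient ever reaches. If SD counts and need not last, a patient who is stable at week 8 and has PD at week 16 enters the numerator on equal terms with a lasting partial response. With scans 8 weeks apart, many patients with slowly growing tumors will be stable at the first scan whatever the drug does. The primary rate then mixes drug effect with natural history, and a single-arm trial has no control group to separate them.

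Durability also matters to the trial's rationale. Section 1.1 notes of sunitinib that "most patients who experienced clinical benefits, later developed tumor progression", and it proposes that adding MET inhibition may prevent such resistance. A status that one week-8 scan can secure says little about that.

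At stake is what a reader can conclude from the headline rate. A figure of 70% or 80% reported as a response rate could come from an active drug or from slow disease.

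**Working it through.** **The plan's own figure.** Wald interval, p ± 1.96 × √(p(1 − p)/n), with p = 0.45:

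- n = 14: 0.45 ± 1.96 × √(0.45 × 0.55/14) = 0.45 ± 0.261, or 18.9% to 71.1%.
- n = 8: 0.45 ± 1.96 × √(0.45 × 0.55/8) = 0.45 ± 0.345, or 10.5% to 79.5%.

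Both match the stated limits, so the arithmetic is not at fault. The question is what the rate measures.

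**Inputs for the check.**

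- Scan times (Section 5.5): 8 weeks = 1.84 months; 24 weeks = 5.52 months.
- Untreated median progression-free survival (PFS) in this disease: not in the documents, so a range of 2 to 12 months is assumed.
- The only placebo figure is in Section 1.2.3.1: a median of 4.0 months and a 0% response rate in the medullary thyroid cancer (MTC) phase 3 trial. In that trial, "Subjects were required to have documented radiographic disease progression per mRECIST within 14 months prior to randomization". The present trial asks for progression within 12 months (Section 4.1), a similar window in a different tumor.

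**A check without a model.** By definition of the median, about half of that placebo arm was progression-free at 4.0 months, so at least half was progression-free at 1.84 months. A group with no objective response would already score 50% or more under the written rule.

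**With exponential PFS.** An inactive drug produces no CR or PR, so its expected rate is P(no PD by t) = 2^(−t/median). For a 4-month median this is 2^(−1.84/4) = 0.727 at week 8 and 2^(−5.52/4) = 0.384 at week 24.

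| Assumed untreated median (months) | Rate as written (SD at week 8 counts) | Rate if SD must last to week 24 |
|---|---|---|
| 2 | 52.9% | 14.8% |
| 3 | 65.4% | 27.9% |
| 4 | 72.7% | 38.4% |
| 6 | 80.9% | 52.9% |
| 12 | 89.9% | 72.7% |

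If 10% or 20% of patients were not evaluable, the 72.7% would become 72.7 × 0.9 = 65.4% or 72.7 × 0.8 = 58.2%.

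**Where an inactive drug reaches 45%.** Solving for the median gives t × ln 2/(−ln 0.45). At week 8 this is 1.84 × 0.693/0.799 = 1.60 months; at week 24 it is 5.52 × 0.693/0.799 = 4.79 months. The 45% serves here only as a reference level.

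**The sunitinib series.** 8/17 = 47.1%, of which partial responses are 3/17 = 17.6% and prolonged stabilizations 5/17 = 29.4%. The total is near 45%, but it counted only stabilization described as prolonged, with no length in months. Four of the patients who benefited had skeletal metastases only, so 47% is not purely a measurable-disease rate.

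**The case against.** The strongest reply is that 45% is not a bar. It only illustrates interval width, and the trial estimates a rate without testing it. A reader might infer that an inactive drug would pass this trial; the documents do not support that, because there is nothing to pass. Precision is not harmed either: at 72.7% the same formula gives about ±23 points, against ±26 at 45%. This stands, and it limits the harm to interpretation.

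A reader might also infer that the 45% was taken from the sunitinib 47%, so that the trial plans for one quantity and measures another. The figures are close, but no section states the link, and the undefined length of prolonged stabilization means that any mismatch cannot be sized.

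Durability is partly covered elsewhere. PFS at one year is the first secondary endpoint, with Kaplan-Meier curves, and categorical variables will be tabulated, so CR, PR and SD could be shown separately. But the PFS endpoint is secondary and pools both branches, and a separate table of response categories is possible without being required. Neither repairs the primary rate.

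The choice of 24 weeks is not dictated by the documents. Their summaries of other trials use several horizons: disease control at week 12 and at 24 weeks, best response at week 16, and SD of at least 6 months. This stands. Week 24 is proposed because the scan is already scheduled and the separation is useful.

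Finally, counting every PD by week 24 as failure would turn best overall response into a landmark progression-free rate, because a PR at week 8 followed by PD would be lost. This also stands, and the duration rule should therefore apply to SD only.

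**Conclusion.** The point holds as a defect in the definition of the primary endpoint. Followed as written, the plan yields a rate that barely separates drug activity from natural history: about 53% to 90% on an inactive drug for untreated medians of 2 to 12 months. Requiring SD to last 24 weeks lowers this to about 15% to 73%.

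These figures assume exponential PFS, no tumor shrinkage on an inactive drug, and complete scans. The 73% against 38% contrast comes from one assumed curve with an MTC median. It should not be read as an estimate for pheochromocytoma and paraganglioma, for which the documents give no untreated PFS. The direction of the result holds across the whole range shown.

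A duration rule helps but is not a complete remedy. With an untreated median of about 5 months or longer, an inactive drug would still reach 45% or more, so CR plus PR must also be visible on its own.

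**What to change.** In the synopsis, Section 2.2.1 and Section 7:

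- Count CR or PR at any time as response.
- Count SD only if there is no PD through the scheduled week-24 scan.
- Keep in the denominator, as non-responders, patients who progress earlier without CR or PR and patients without the needed assessment.
- Label the composite disease control (clinical benefit).
- Report CR plus PR alone, and SD of any duration, as separate lines, each with a 95% confidence interval.
- State which definition the 45% illustration refers to.

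This changes wording only; no scan is added. The costs are a lower headline rate, a result up to 16 weeks later for the last patient (week 24 instead of week 8), and the incomplete protection in slow disease described above.

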7.1 Analysis Population

7.1.1 Safety Population

The safety population will consist of all subjects who receive any amount of study treatment.

7.2 Safety Analysis

Safety will be assessed by evaluation of AEs. All safety analyses will be performed using the safety population.

7.2.1 Adverse Events

Adverse event terms recorded on the CRFs will be mapped to preferred terms using the National Cancer Institute (NCI) CTCAE v4.0. Seriousness, severity grade and relationship to study treatment will be assessed by the investigator. Severity grade will be defined by the National Cancer Institute (NCI) CTCAE v4.0. Listings of AEs will be provided.

7.3 Sample Size

The sample size will be approximately 22 subjects.

8 DATA QUALITY ASSURANCE

Accurate and reliable data collection will be ensured by verification and crosscheck of the CRFs against the investigator's records by the study monitor (source document verification).

9 ETHICAL ASPECTS

9.1 Local Regulations

The study must fully adhere to the principles outlined in "Guideline for Good Clinical Practice" (GCP) ICH E6 Tripartite Guideline (January 1997). The investigator will ensure that the conduct of the study complies with the basic principles of GCP as outlined in the current version of 21 Code of Federal Regulations, subpart D, Part 312, "Responsibilities of Sponsors and Investigators" Part 50, "Protection of Human Subjects" and Part 56, "Institutional Review Boards."

9.2 Informed Consent

It is the responsibility of the investigator, or a person designated by the investigator, to obtain written informed consent from each subject participating in this study after adequate explanation of the aims, methods, anticipated benefits, and potential hazards of the study. In the case where the subject is unable to read, an impartial witness should be present during the entire informed consent discussion. After the subject has orally

consented to participation in the trial, the witness's signature on the form will attest that the information in the consent form was accurately explained and understood.

The CRF for this study contains a section for documenting informed subject consent, and this must be completed appropriately. If new safety information results in significant changes in the risk/benefit assessment, the consent form should be reviewed and updated as necessary. All subjects (including those already being treated) should be informed of the new information, should be given a copy of the revised form, and should give their consent to continue in the study.

9.3 Institutional Review Board/Ethics Committee

This study is being conducted under a United States Investigational New Drug application or other Clinical Trial Application, as appropriate. This protocol (and any modifications) and appropriate consent procedures must be reviewed and approved by an IRB/EC. This board must operate in accordance with current local, regional, and federal regulations. The investigator will send a letter or certificate of IRB/EC approval to Exelixis (or designee) before subject enrollment and whenever subsequent modifications to the protocol are made.

9.4 Future Use of Patient Samples

No samples for anything other than safety testing will be collected during this study.

10 CONDITIONS FOR MODIFYING THE PROTOCOL

Protocol modifications may be made and will be prepared, reviewed, and approved by representatives of the investigator.

All protocol modifications must be submitted to the IRB/EC for information and approval in accordance with local requirements and to regulatory agencies if required. Approval must be obtained before any changes can be implemented, except for changes necessary to eliminate an immediate hazard to study subjects or those that involve only logistical or administrative aspects of the trial (eg, change in monitor or change of telephone number).

11 CONDITIONS FOR TERMINATING THE STUDY

Exelixis and MD Anderson Cancer Center/IND Office reserves the right to terminate the study, and investigators reserve the right to terminate their participation in the study, at any time. Should this be necessary, Exelixis and MD Anderson Cancer Center/IND Office and the investigator will arrange the procedures on an individual study basis after

review and consultation. In terminating the study, Exelixis and MD Anderson Cancer Center/IND Office and the investigator will ensure that adequate consideration is given to the protection of the subjects' interests.

12 STUDY DOCUMENTATION AND RECORDKEEPING

12.1 Source Documents and Background Data

Upon request, the investigator will supply its licensees and collaborators with any required background data from the study documentation or clinic records. This is particularly important when errors in data transcription are suspected. In case of special problems or governmental queries or requests for audit inspections, it is also necessary to have access to the complete study records, provided that subject confidentiality is protected.

